Evaluating a Patient-Centered Tool to Help
Medicare Beneficiaries Choose Prescription Drug
Plans (CHOICE)

NCT02895295

September 23, 2016

[name], Principal Investigator
Stanford University
Stanford, California 94305

1. Protocol

A. Abstract

To obtain publicly subsidized insurance coverage for prescription drugs, Medicare beneficiaries must choose among the private plans offering coverage in their geographic area. While Part D has reduced beneficiary spending on and lowered prices for prescription drugs, Medicare beneficiaries consistently report that choosing a plan is difficult, time consuming and unpleasant.

In this project, we test the effects of a patient-centered Medicare Part D prescription drug decision tool that is scalable and patient-centered and builds on research indicating that many people would like expert assistance in making this choice. Our main objectives are to determine whether providing Medicare beneficiaries with a patient-centered decision tool and whether providing an expert recommendation of a particular plan improve decision outcomes relative to providing them with access to publicly available tools.

B. Specific Aims

Aim 1: To determine whether providing Medicare beneficiaries with a patient-centered decision tool to help them choose among plans improves outcomes for patients including a greater likelihood of changing a plan, better coverage for prescribed drugs, lower decisional conflict when choosing plans, and greater satisfaction with the choice process relative to current practice.

Aim 2: To determine whether providing people with personalized expert plan recommendations improves outcomes for patients including a greater likelihood of changing a plan, better coverage for prescribed drugs, lower decisional conflict when choosing plans, and greater satisfaction with the choice process relative to current practice and relative to a similar tool without such recommendations.

Aim 3: To determine what types of older adults are likely to use an internet-based tool for health plan choice.

C. Study Overview

In this study, we will test the effectiveness of two versions of a web-based tool to help people choose among Part D plans (Treatments A and B) relative to each other and relative to standard care (Control). Both treatment arms will incorporate simplified design and automated importation of an individual's drugs relative to standard care. The treatment arms will vary based on whether they provide expert guidance on recommended plans. In the control arm, study participants will be directed to the existing, publicly available Medicare.gov website and will receive instructions on how to download their drugs from the Palo Alto Medical Foundation (PAMF) patient-facing EMR (myhealthonline). Our study sample will include PAMF patients who were enrolled in Part D plans during the 2016 enrollment period. Prior to the 2017 open enrollment period (October 15 to December 7, 2016), we will invite a subset of PAMF patients enrolled in Part D plan to participate in a study examining the effectiveness of decision tools that provide personalized information on the financial implications of enrolling in different Part D plans.

For aims 1 and 2, the *primary study outcomes* will be:

- 1) Plan switching
- 2) Change in generosity of coverage of prescription drugs

- 3) Satisfaction with the choice process
- 4) Decisional conflict

Secondary study outcomes for aims 1 and 2

- 5) Enrollment in an expert-recommended plan
- 6) Difficulty choosing a plan
- 7) Confidence in choosing a plan
- 8) How much do you like the plan you chose
- 9) Satisfaction with chosen plan (people found this difficult)
- 10) Knowledge of the Medicare Part D prescription drug benefit?

For aim 3, we will analyze how the following patient characteristics influence enrollment in the trial and take-up of the treatment among those randomized to the treatment arm:

- 1) Prescription drug profile
- 2) Age
- 3) Use of myhealthonline

We will measure the primary study outcomes using a combination of administrative data and a post open enrollment survey administered to all study participants. We will also collect information on individual characteristics at the time of enrollment in the study and implement a survey examining use of the intervention tool to assess patient experience at the time of use.

D. Background

Medicare beneficiaries consistently report that choosing a plan is difficult, time consuming and unpleasant. In our preliminary qualitative work, older adults said that these difficulties cause them to seek assistance from trusted authorities like brokers and counselors and sometimes even to avoid changing their plan altogether.

Research on plan choice is consistent with these observations. People are often not enrolled in the plan that would cover their drugs at the lowest price and rarely change plans even when there are alternatives that provide coverage at a lower cost. In addition, brands have strong effects on individual choices, and it is not clear whether particular brands provide real value for consumers or simply serve as a decision short-cut.

Research has also shown, however, that personalized information on the financial implications of enrolling in different plans can influence plan choice. Using a relatively simple, paper-based intervention, Kling et al. demonstrate that, when people received a letter with personalized information about the cost of enrolling in different plans, they were more likely to switch plans than those who received information about the availability of this type of information on the Centers for Medicaid and Medicare Services (CMS) website. While this trial shows potential for decision tools to improve outcomes in this area, many questions remain on how best to provide this type of information to consumers. Although publicly available tools are available to Medicare beneficiaries to help them make these types of decisions, evidence suggests that they rarely use this source of information.

One potential barrier is that the currently available tools are difficult for beneficiaries to use. In our ethnographic research observing Medicare beneficiaries using the Medicare.gov website, we identified two limitations of the existing tool: 1) it is difficult for beneficiaries to customize the information with their personal drug histories, and 2) the most commonly used tool (Medicare.gov plan calculator) is difficult for people to navigate and use. We have developed a tool that addresses these barriers by importing beneficiaries' information about drug use directly into the tool and by creating a patient interface that incorporates modern design concepts and patient input to make the tool accessible and effective for beneficiary decision making.

In our ethnographic study, older adults also expressed interest in having additional support, often indicating they would like the help of an expert, such as an insurance broker or other type of knowledgeable individuals.

Our study is based on the hypothesis that these barriers create switching costs for beneficiaries and that removing these barriers would lower switching costs making beneficiaries more likely to evaluate their alternatives and to enroll in plans that provide better coverage for the drugs they are likely to use. We also hypothesize that reducing switching costs, particularly by providing expert recommendations, will reduce decisional conflict and create greater satisfaction with the choice process.

While the tool we have designed in partnership with patient stakeholders is easier to use than the Medicare.gov website, it provides less detail on how the different plans cover particular types of drugs. In our qualitative work examining the use of the first version of our tool, we found that its simplicity was more attractive to some people than others. Thus, we will examine particular characteristics of individuals including numeracy, "do-it-yourselfness", and satisficer/maximizer behavior influence how people evaluate the decision process in the different tools.

A final issue in this context is whether simply providing access to web-based decision support tools is likely to assist the types of people who experience the greatest difficulty in decision-making. We will examine the take-up of decision support in this setting to determine how well targeted it is by analyzing who chooses to enroll in our trial and among those who enroll, who uses the study intervention.

E. Participants

Our study population will include PAMF patients aged 66 to 85 who were enrolled in Part D coverage during 2016. We plan to have a final study sample of at least 915 people with complete data on study outcomes.

F. Screening

We will prescreen patients using administrative data to identify potential study participants based on whether they are enrolled in Medicare, their age (66-85), whether they live in the primary PAMF service area (county=Santa Clara, San Mateo, Santa Cruz, and Alameda), and whether they have active medication orders in the PAMF EMR. We will also exclude patients enrolled in MediCal or a Medicare Advantage plan in 2016. In preliminary analyses, we have identified 46,525 PAMF patients who meet these criteria.

An important sampling issue for our study is whether people are married or cohabitating. Randomizing people who are cohabitating to different treatment arms could lead to cross-arm contamination, potentially diluting the treatment effects. We will prescreen patients for cohabitation/marital status based on patient residence and phone number. We will then randomly choose one member of each household to participate in the intervention. In our preliminary analysis, we excluded an additional 7,659 people using this method. Because this represents fewer people than we would have expected based on national rates of marriage among older adults, we will also screen for cohabitation when recruiting. Again, based on our preliminary analysis, there will be 38,866 remaining patients eligible for recruitment.

G. Recruitment

We will recruit a subset of those patients eligible for recruitment with a goal of obtaining complete study data from 915 patients. We will identify a set of patients for recruitment by randomly choosing a subset of approximately 10,500 patients from those who are eligible for recruitment. For the patients targeted for recruited (recruitment sample), we will send them a letter in August introducing the study and inviting them to participate. The letter will inform the respondent that they have been selected to participate in a study of the effects of providing personalized information on Medicare Part D prescription drug plans and that they will be randomized to different arms representing different ways of providing that information, that participation in the intervention will allow them to easily access information from PAMF on the prescription drugs they are currently using. The e-mail will also inform the patients that they will receive a \$50 electronic Target gift certificate at the end of the open enrollment period for participating in the study following the completion of a questionnaire. The letter will direct participants to a website (enrollment portal) where they can check if they meet the eligibility criteria and, if so, enroll in the study and provide informed consent.

The initial invitation will include a study ID that the participant will use to enter the enrollment portal. This ID will be used as their study ID throughout the study and will be used to link data from their medical records to data gathered as part of the study. The enrollment portal will have 4 functions:

1. Eligibility verification - When patients log into the application, they will verify their name and address as well as their eligibility to participate in the study based on age, part d enrollment, and single representative from their household. (We will not exclude people from accessing the tool based on the single representative but will exclude them from data analysis). They will also identify the Part D plan in which they are currently enrolled.
2. Informed consent
3. Collect contact information - Consented participants will provide their e-mail address, using double-entry verification, and will be informed that further communication regarding the study will be by e-mail rather than by mail.
4. Pre-enrollment survey (Survey 1) - We will ask a few questions intended to provide information on individual characteristics of interest for the purpose of data analysis.

We will consider people who consent through the enrollment app as the “enrolled” population. The enrolled population will be randomly assigned to one of three arms (Treatment A, Treatment B or Control). Within 2 days after subjects enroll, we will send them by e-mail a letter that includes their study ID and information on how to access the tool, including the location of the website, when it will be available and log-in instructions. They will use the study ID to log into the website when open

enrollment begins. Shortly before and close to the end of open enrollment, we will send them another reminder with the same information.

We will provide support to study participants in the form of an e-mail address and a phone number they can call. This information will be available in our study tool, the control arm screen and the consent form. We will indicate that they will receive a response within 48 business hours.

Table 1: Recruitment Objectives

Sample Name	Category	Assumptions	Number of Study Subjects
Eligible for Recruitment	Eligible for recruitment		38,866
Recruited Sample	Chosen for mail recruitment	Derived from assumptions below	10,417
	Check for Eligibility	20% of those who contacted by mail check their eligibility	2,083
Enrolled Population	Enroll in Study	Assume 40% attrition among those who access enrollment app	1,250
Study Sample	Complete final survey	Assume 80% of those enrolling complete final survey	1,000
Objective based on sample size calculation		based on 3 arms of 305 each	915

Source: trial protocol tables google sheet – recruitment objectives

We will identify a set of patients for recruitment by randomly choosing a subset of approximately 10,500 patients from those who are eligible for recruitment. We estimate that 20% of those contacted will choose to access the enrollment portal. Among those who access the enrollment portal, we estimate 30% attrition based on ineligibility or lack of consent. Finally, we estimate that 60% of those who enroll will complete the final survey in January. The table above identifies the effects of each these assumptions on our final sample size.

We estimate the size of the final study sample will be 1,000 people with 333 assigned to each arm. Our sample size calculations indicate that we need 305 people per arm to have adequate sample size (see detail under section “assessments”).

H. Randomization

We will randomize those who enroll in the study into two treatment arms and one control arm in which they will be directed to different on-line tools. Participants will be randomized at the time they enroll by simply assigning them sequentially to the three arms as they consent.

I. Retention

While our study period is relatively short, only lasting throughout the open enrollment period, a key issue in retention is encouraging people to participate in a survey at the end of the open enrollment

period. Study participants will receive their \$50 gift certificate from Target after completing the post open enrollment survey in January.

J. Intervention

The study has two types of interventions. The primary intervention is access to a decision tool (Aim 1) and the second is access to a decision tool with expert recommendations (Aim 2). People who enroll in the study will be randomized to one of three arms – two treatment and one control arm. People randomized to the treatment arms will receive a one of two versions of an on-line decision tool that automatically imports information on their prescription drug use from an electronic medical record into a decision tool developed as part of the study. In Treatment Arm A (expert recommendations), the tool will provide people with a score for each plan using an algorithm for generating expert recommendations based on the individual’s prescription drug usage and the characteristics of the different plans. In Treatment Arm B (individual analysis), we will provide information on each of the characteristics underlying the expert recommendation but not the recommendation itself. In the control arm, people will receive information on how to download their prescription drug information from the electronic medical record and how to access the Medicare.gov Plan Finder tool.

The calculations underlying the calculator as well as the expert recommendations will be powered by software we have purchased from a private third party, [REDACTED]. [REDACTED] produces software that allows a user to enter electronically a set of prescription drugs and returns information on associated out-of-pocket spending and the premium for each Part D plan available to the beneficiary. [REDACTED] also provides a “score” which represents a weighted average of the person’s estimated out-of-pocket spending and premium and the plan’s consumer satisfaction rating. Our user interface will, in turn, present this information to study participants in a patient-centered way and will manipulate the information in the two study arms as described above.

Participants will not actually enroll through our calculator. Instead we will direct participants to the appropriate company website or to the Medicare website where they can enroll.

The decision tool will be available throughout the open enrollment period.

K. Assessments

The study outcomes will be based on both primary data collection and administrative data sources. The sample size was chosen to adequately power the primary study outcomes.

Table 2: Summary of Outcome Measures for Comparative Effectiveness Evaluation

Note: Primary study outcomes are italicized and bold.

Outcome Type		Measures	Data Source
Patient Satisfaction	Aims 1 and 2	• Satisfaction with choice process	Post-enrollment survey (primary)
Plan Choice	Aims 1 and 2	• Change in Part D plan chosen	2016 plan from enrollment app and 2017 plan from post

			open enrollment survey. Also question in post enrollment survey about “did they change their plan?”
	Aims 1, and 2	
 • Indicator of enrollment in lowest cost plan* • Indicator of enrollment in expert chosen plan* 	2017 plan from post open enrollment survey and information on OOP cost from [REDACTED] collected in admin panel.
Spending on prescription drugs	Aims 1, and 2.	
 • Difference in spending between lowest cost plan and chosen plan* 	[REDACTED] information for all plans and indicator of which plan was chosen from post open enrollment survey.
	Aims 1 and 2	
 • Difference in spending between 2016 plan and 2017 plan based on initial drug list.* 
Note: this address whether they switched to a lower cost plan
	[REDACTED] information for all plans and indicator of which plan was chosen from post open enrollment survey and which plan they were initially enrolled in from enrollment app.
Choice Experience	Aims 1 and 2	
 • Decisional Conflict • Knowledge about Part D program • Sources of information used • Time spent making decision 	Post-enrollment survey
		
 • How satisfied were you with the process of choosing a plan? • Decision confidence • Decision conflict • Choice knowledge – understanding of features of chosen plan • Right amount of information • Define user monitoring outcomes 	Intervention survey

* Note that calculating these variables requires a drug list for each person. For all people, we can construct an initial drug list based on the data in the EMR. For a subset of people who we observe using the tool, we can construct a revised drug list based on their activity in the tool. All these outcomes are based on the initial drug list.

L. Data Management

See data flow chart document.

M. Study Timeline

May 31 – Large dataset of test data

June 30 – UI changes implemented

July 15 – refreshed study data available to developer

July 31 – administrative console implemented

August 1 – Invitations mailed to participant

August 1 – October 14 – recruitment and enrollment

August 1 – website available with “coming soon” information

August 1-August 30 – complete testing and list of changes to developer

September 30 – all changes implemented

October 1 – generate dataset of all [REDACTED] information for everyone chosen for recruitment.

October 1 – October 12 – final verification of functionality

October 15 – e-mail reminder (exact date depends on when tool is refreshed with 2016 open enrollment information)

October 15 – December 7 – Open enrollment – tool available

December 8 – e-mail follow up survey

January 4 – e-mail reminder about survey

December 8 – January 15 – follow up survey open

January 16 – e-mail gift cards

2. Statistical Plan

Sample size calculations:

	Hypothesis						
Outcome	Relative to control, treatment groups will have:	Baseline rate	SD	Change	Power	N per group	Notes:

Plan switching	Higher rates of plan switching	13.6		8.704	80%	305	Kling et al find 28% of people in treatment group relative to 17% in control. Ketcham et al 2013 find relative high rates of switching among new enrollees - 33% between 2009 and 2010 and that switching rates increased over time. KFF (2103) finds 13.6 among all ages in PDP plans. Change is Kling effect of 65% change applied to KFF baseline rate.
Satisfaction with choice process	Greater satisfaction with the choice process	2.6	1.03	0.6	80%	50	Scale of 1-4 in preliminary study with 1 as very satisfied. Data represent means of medicare versus all vendus arms where medicare is the baseline.
Decisional conflict	Less decisional conflict						
Coverage	enrollment in plans that coverage current drugs more generously	368	286	74	80%	236	Based on Kling et al
Coverage (alternative)	Increase in coverage generosity from last years to this years plan	-129	588.42	-543	80%	20	Based on Fall 2015 Results

Analyses:

For aims 1 and 2, we will compare outcomes between each treatment group and the control group, defining the study population as those who enroll in the study through the enrollment portal and are randomly assigned to a study arm. The main focus of our analyses will be the comparison of the Expert arm relative to the control arm. We will calculate differences in means and proportions using t-tests and chi-squared tests based on the type of study outcome. We will also test the expert arm relative to the treatment arm without expert recommendations to identify the independent effect of expert recommendations. We will develop unadjusted estimates of the treatment effect as well as estimates adjusting for individual characteristics from survey and administrative data.

For aim 3, we will analyze how individual characteristics affect whether people choose to participate in the trial (take up of our invitation to participate). The key study variables will include age, use of myhealthonline, and prescription drug profile.

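### People who are not their household's single representative still get a study tool and only their data are dropped, which leaves a retained partner exposed to another arm; the Statistical Plan's study population omits the exclusion.

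*Combined protocol and SAP*

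**What the plan says.** Section 1.F (Screening) names the risk: "Randomizing people who are cohabitating to different treatment arms could lead to cross-arm contamination, potentially diluting the treatment effects". The first safeguard is a prescreen on residence and phone number, after which "We will then randomly choose one member of each household to participate in the intervention". The prescreen removed 7,659 of 46,525 patients. The protocol regards this as "fewer people than we would have expected based on national rates of marriage among older adults, we will also screen for cohabitation when recruiting".

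Section 1.G (Recruitment) puts that second screen in the enrollment portal. Patients verify their "eligibility to participate in the study based on age, part d enrollment, and single representative from their household". The rule for those who fail the household item follows in parentheses: "We will not exclude people from accessing the tool based on the single representative but will exclude them from data analysis". Earlier in the same section, the invitation letter is said to send people to a website where they can "check if they meet the eligibility criteria and, if so, enroll in the study and provide informed consent".

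Section 1.G continues: "We will consider people who consent through the enrollment app as the “enrolled” population". All of these people are assigned to one of the three arms. Section 1.H (Randomization) does this in sequence as individuals consent, and neither section has a household rule.

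The Statistical Plan (Analyses) compares arms "defining the study population as those who enroll in the study through the enrollment portal and are randomly assigned to a study arm". It mentions no household exclusion.

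**The concern.** Contamination between partners happens through what is seen at home. Dropping the second member's data leaves unchanged what the first member saw. A Control participant whose spouse has the expert-recommendation tool stays in the analysis, and any carry-over pulls the arms together.

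There is also a problem with the analysis set. An analyst working from section 1.G removes flagged people; one working from the Statistical Plan keeps them. In the second case, t-tests and chi-squared tests treat two people who may share one decision as independent. The choice should be fixed before outcomes are seen.

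**Working it through.** **Where the sections meet.** Section 1.F wants one person per household because partners in different arms dilute the effect. Section 1.G admits the second person to the tool and removes only that person's data. Sections 1.G and 1.H describe no way to a tool except consent and individual assignment. The Statistical Plan counts everyone assigned. The documents do not say how a flagged person's tool version is chosen, or whether the remaining household member is also dropped.

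**The plan's own figure.** Plan switching at 13.6% versus 13.6 + 8.704 = 22.304%, 80% power, two-sided alpha 0.05 (assumed; none is stated), pooled variance, no continuity correction: 305 per arm, as stated. Power is 80.1% at 305 per arm and 83.5% at the expected 333.

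**How many pairs.** Inputs from sections 1.F and 1.G: 46,525 screened, 7,659 removed, 46,525 − 7,659 = 38,866 left, 10,417 mailed, 1,250 enrolled.

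Assumed: a share s = 40-60% of the 46,525 live with another eligible patient. A mailed partner enrolls with probability e, from 12% (Table 1: 20% × 60%) to 50% (assumed, for couples who act together).

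- People in pairs that the prescreen missed: s × 46,525 − 2 × 7,659. At s = 0.4 this is 18,610 − 15,318 = 3,292 (8.5% of 38,866). At s = 0.6 it is 27,915 − 15,318 = 12,597 (32.4%).
- Chance that the partner is mailed: 10,417 / 38,866 = 26.8%.
- Share of enrolled people with an enrolled partner: 8.5% × 26.8% × 12% = 0.27% at the low end; 32.4% × 26.8% × 50% = 4.3% at the high end. Of 1,250, that is about 3.4 to 54 people, counting both members of each couple.

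**From people to contaminated controls.** Under section 1.G one member of each couple is dropped. If partners' arms are unrelated, two thirds of couples are in different arms, and one third of the retained members of those couples are controls.

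| | Low | High |
|---|---|---|
| Enrolled people in couples | 3.4 | 54 |
| Retained (÷ 2) | 1.7 | 27 |
| Partner in another arm (× 2/3) | 1.1 | 18 |
| Of these, controls (÷ 3) | 0.4 | 6 |
| Share of 1,250 / 3 = 417 controls | 0.09% | 1.4% |

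**Effect on power.** Take the worst case, in which each such control switches at the full treatment rate. At 1.4% the control rate is 13.6 + 0.014 × 8.704, about 13.7%. Power falls from 80.1% to 78.9% at 305 per arm and from 83.5% to 82.3% at 333. At the low end the loss is about 0.1 point.

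**Two variations at the high end.**
- If the Statistical Plan's population is used and nobody is dropped, the share of controls with a treated partner is 4.3% × 2/3 = 2.9%, and power at 305 per arm is 77.5%.
- Allocation is sequential, so partners who consent directly one after the other always land in different arms. If every couple did so, 27 / 3 = 9 retained controls (2.2%) would be affected, and power at 305 per arm would be 78.2%.

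**The case against.** Much of the case on the other side is sound.

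- **Safeguards.** The prescreen comes first, only 26.8% of the remaining pool is mailed, and portal entry needs the study ID from the invitation. A second household member arrives only if the prescreen missed the pair and both were drawn. This stands, and it is why the numbers are small.
- **Personalised tool.** Under section 1.J the tool works from the individual's own drugs, so a spouse's screen may carry over only partly. This stands too: full carry-over is a worst case. The protocol itself, however, treats the contamination as worth preventing.
- **Other readings of the rule.** Household status is an eligibility item, and the letter has only eligible people enroll. The parenthesis speaks of access, not assignment. If flagged people were never enrolled, the Statistical Plan would already omit them; if the exclusion covered the whole household, no exposed partner would be retained. One could also read section 1.G as a specific rule that qualifies the Statistical Plan's general one. The text settles none of this, and no separate access route is described. That makes the wording ambiguous and leaves the need to reconcile it.

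Three stronger readings are tempting but not supported. A reader might infer that all of the roughly 3 to 54 people are contaminated in the analysis; that figure counts both partners, one of whom section 1.G drops. A reader might infer that Table 1 includes flagged people in its 1,250 and 1,000; section 1.G attributes part of the portal attrition to ineligibility, so they may already be out. A reader might infer that the exclusion biases the arm comparison; status is recorded before assignment, so it need not.

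**Conclusion.** The concern holds in a limited form. Excluding only the second member's data does not remove the exposure that section 1.F is concerned with, and section 1.G and the Statistical Plan state different analysis populations. The second point does not depend on how many couples there are.

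The numerical effect is small and runs toward no difference: about 0.1-1.4% of retained controls with a partner in a treatment arm, and about 1 point of power at most. This rests on assumed cohabitation and partner-enrollment rates, unrelated arms within couples, full carry-over and a two-sided alpha of 0.05. Back-to-back consent by every couple would raise the high-end loss to just under 2 points. The 305 per arm is not in error.

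**What to change.** 1. **Portal.** When a person is flagged as not the single representative, ask for the study ID of the household member already enrolled, with the verified address as back-up. Give that member's tool version outside the allocation sequence. Address alone would be a weak link, because these are pairs that residence and phone matching already missed.
2. **Statistical Plan, Analyses.** Define the study population as all those assigned who were recorded in the portal, before assignment, as the single representative of their household.
3. **Table 1.** State whether flagged people fall in the eligibility attrition or in the 1,250 enrolled.

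Open access to the tool is kept. The cost is a small portal change, a few sentences, and possibly slightly smaller counts. Table 1 leaves 1,000 − 915 = 85 to spare, but the attrition rates in the text below it (30% attrition, 60% completion) give 10,417 × 0.2 × 0.7 × 0.6 = 875, so that margin should not be taken for granted. Some pairs will still be missed.

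### Table 1 and the text below it give different recruitment rates: 40% attrition and 80% completion yield the stated 1,000 completers, while 30% and 60% yield only 875 to 882, below the 915 goal

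*Combined protocol and SAP*

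**What the plan says.** Table 1 in section 1.G follows recruitment from letters mailed to surveys completed. Of 10,417 people mailed, 20% check their eligibility (2,083). For the next step the table says "Assume 40% attrition among those who access enrollment app", which leaves 1,250 enrolled. For the last it says "Assume 80% of those enrolling complete final survey", which leaves 1,000. The 10,417 is annotated "Derived from assumptions below".

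The paragraph directly under the table mails approximately 10,500 letters and keeps the 20%, but changes the next two rates. It says "Among those who access the enrollment portal, we estimate 30% attrition based on ineligibility or lack of consent" and "Finally, we estimate that 60% of those who enroll will complete the final survey in January". It continues: "The table above identifies the effects of each these assumptions on our final sample size". It then concludes: "We estimate the size of the final study sample will be 1,000 people with 333 assigned to each arm".

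The target is set in section 1.E: "We plan to have a final study sample of at least 915 people with complete data on study outcomes". Table 1 and section 1.G repeat it as three arms of 305.

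**The concern.** The two sets describe the same steps, portal to enrollment and enrollment to final survey, and both are current text. The paragraph claims to describe the table, yet its rates are not the table's and cannot produce the 1,000 that it states.

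Two things depend on which set is meant.

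- **Expected sample.** One set puts the trial above its goal of 915 and the other puts it below.
- **Expected loss of outcome data.** One set plans for 20% of randomized participants without a final survey, the other for 40%. Table 2 (section 1.K) takes the 2017 plan, and with it plan switching and the spending gap to the cheapest plan, from the post open enrollment survey. Satisfaction with the choice process and decisional conflict come from the same survey. A missing survey therefore means missing primary outcomes, while the Analyses part of section 2 defines the study population as everyone enrolled and randomized.

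**Working it through.** **Inputs.** Letters: 10,417 (Table 1) or approximately 10,500 (text). Portal access: 20% in both. Attrition: 40% (Table 1) or 30% (text). Completion: 80% (Table 1) or 60% (text). Goal: 915, or 305 per arm. Plan switching (section 2): baseline 13.6%, change 8.704 points, power 80%. No alpha is stated; two-sided 0.05 is assumed.

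**Formula.** Completers = letters × access × (1 − attrition) × completion.

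**The plan's own figure.** 10,417 × 0.20 = 2,083; × 0.60 = 1,250; × 0.80 = 1,000; ÷ 3 = 333 per arm. Backwards, 1,000 / (0.80 × 0.60 × 0.20) = 10,417. Table 1 is internally consistent.

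**All combinations.**

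| Attrition / completion | 10,417 letters | 10,500 letters |
|---|---|---|
| 40% / 80% (Table 1) | 1,000 | 1,008 |
| 30% / 60% (text) | 875 | 882 |
| 40% / 60% (mixed) | 750 | 756 |
| 30% / 80% (mixed) | 1,167 | 1,176 |

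Only Table 1's pair gives about 1,000. The text's pair falls about 12% short of it, too much for rounding.

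**Detail for the text's rates.**

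- 10,417 × 0.20 × 0.70 = 1,458 enrolled; × 0.60 = 875; ÷ 3 = about 292 per arm; 915 − 875 = 40 short.
- 10,500 × 0.20 × 0.70 = 1,470 enrolled; × 0.60 = 882; ÷ 3 = 294 per arm; 915 − 882 = 33 short.

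**Missing final surveys.** Table 1: 1,250 − 1,000 = 250 (20%). Text: 1,458 − 875 = 583, or 1,470 − 882 = 588 (40%).

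**Power for plan switching.** p1 = 0.136, p2 = 0.22304, mean p = 0.17952, difference d = 0.08704.

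n per arm = [1.960 × √(2 × 0.17952 × 0.82048) + 0.8416 × √(0.136 × 0.864 + 0.22304 × 0.77696)]² / 0.08704² = 304.02, so 305.

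This reproduces the plan's 305, which supports the assumed alpha. The same formula gives these powers:

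| Completers per arm | Power |
|---|---|
| 333 (Table 1 rates) | 83.5% |
| 305 (requirement) | 80.1% |
| 294 (text rates, 10,500 letters) | 78.7% |
| 292 (text rates, 10,417 letters) | 78.3% |

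**Other outcomes.** The other stated requirements are 236, 50 and 20 per group, and 292 to 294 exceeds all of them. For coverage (difference 74, SD 286, t-test) power is about 88%.

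**Break-even.** With 30% attrition, 915 is reached when completion is 915 / 1,458 = 62.7% (10,417 letters) or 915 / 1,470 = 62.2% (10,500 letters). At 60% completion, 915 / (0.20 × 0.70 × 0.60) = about 10,893 letters would be needed.

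**The case against.** The strongest reply is that these are two stale percentages left in the prose after the table was updated. The 10,417 back-solves exactly from Table 1's rates, and the approximately 10,500 letters, the 1,000 and the 333 per arm all fit them. On that reading the plan expects 1,000 completers and misses nothing. Even on the other reading the shortfall is about 4% of 915, it costs under 2 points of power on one outcome, and less than 3 points of extra completion would close it. The rates are forecasts, and 38,866 eligible patients leave room to mail more. No test, allocation or required sample size depends on the two percentages.

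Most of this stands. Table 1 is the likelier set, and the power effect is small. But the plan does not say which set governs, and the paragraph offers 1,000 as the result of rates that cannot give it. The difference between 20% and 40% expected loss of survey-based primary outcomes is not small, even though no analysis rule is tied to either rate.

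Mailing more is possible but is not a text correction. The document is dated September 23, 2016, and the timeline in section 1.M mails invitations on August 1 and ends recruitment on October 14.

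**Conclusion.** The concern holds. Two current sets of rates conflict, and only Table 1's supports the stated 1,000. The plan either exceeds its goal by 1,000 − 915 = 85 or misses it by 33 to 40. It expects either 250 participants (20%) or 583 to 588 (40%) without the final survey. The power consequence is confined to plan switching and is about 1.4 to 1.8 points below the 80.1% available at 305 per arm.

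The completer counts need no assumption beyond the documents' own rates. The power figures assume two-sided alpha 0.05, the pooled normal approximation without continuity correction, and completers split equally across arms. This should be fixed, but it does not threaten the design.

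**What to change.** State one set of rates in Table 1 and in the text below it.

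- **If 40% and 80% are meant**, as the other figures suggest, correct the two percentages in the text and leave 1,000 (333 per arm) unchanged.
- **If 30% and 60% are meant**, restate Table 1 and the text as about 1,460 enrolled and about 880 completers (about 294 per arm, about 79% power for plan switching). State an expected loss of 40% for the survey-based primary outcomes, and say openly that the expectation is below the 915 in section 1.E. Raising the mailing to about 10,893 letters would meet 915 at these rates, but that is an operational change.

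Apart from that mailing option, the cost is text only: two percentages in the first case; the table rows, expected sample, power and expected loss in the second. The design, the analysis and the 305 per arm requirement do not change.
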